## **Presentation of Baseline Characteristics and Safety Data**

Baseline characteristics and safety data will be presented as mentioned below. Data captured but not presented as listed or summarized data will be available in the CRFs or the source data capture system.

Demographic and anthropometric data will be listed for all participants in the safety population. Demographic characteristics will be tabulated by treatment (n, mean, median, standard deviation, minimum and maximum for age and BMI; and frequency counts and percentages for race, age groups and sex).

Adverse events (AEs) will be coded using the Medical Dictionary for Regulatory Activities (MedDRA), and listed and summarized by treatment for all participants in the safety population.

Vital signs data will be listed and summarized for all participants in the safety population.

## **List of Tables, Figures and Listings**

The following tables, figures and listings will be provided for inclusion into the mentioned sections of the clinical study report.

### **Tables**

Demographic characteristics

Statistical analyses of ciprofloxacin PK parameters (ANOVA)

Non Parametric Analysis of ciprofloxacin PK parameter

Plasma ciprofloxacin concentration (unit)

Plasma ciprofloxacin PK parameter (unit)

Adverse events summary by treatment

Concomitant Medication summary by treatment

Summary Statistics of Vital Signs Values

Summary Statistics of Chemistry Values.

Summary Statistics of Haematology Values.

**Figures**

Plasma ciprofloxacin arithmetic and geometric mean concentrations (unit)

Median concentration vs. Time for ciprofloxacin

Combined individual plasma ciprofloxacin concentrations (unit)

Individual plasma ciprofloxacin concentrations (unit) (linear-linear scale and log-linear scale)

Adjusted geometric mean treatment ratio (with 90% CI) for ciprofloxacin

**Listings**

Statistical output

Participant disposition

Randomization

Demography and anthropometry

Adverse events

Concomitant Medication

Vitals Signs

Haematology

Chemistry

Urinalysis

12-ECG Lead

Actual blood sampling times

Plasma ciprofloxacin concentrations (unit)

Plasma ciprofloxacin PK parameters (unit)

The bulleted lists above indicate requirements and are not necessarily the exact names of each table, figure or listing. The naming conventions as provided will be adhered to as far as feasible, but if deemed necessary the name of the output might be changed to fit the data.

## 12.7. Appendix 7: Abbreviations and Trademarks

AE	Adverse Event
ALT	Alanine aminotransferase (SGPT)
APTT	Activated Partial Thromboplastin Time
AST	Aspartate aminotransferase (SGOT)
AUC	Area under concentration-time curve
$AUC_{(0-\infty)}$	Area under the concentration-time curve from time zero (pre-dose) extrapolated to infinite time
$\%AUC_{ex}$	Percentage of $AUC(0-\infty)$ obtained by extrapolation
$AUC_{(0-t)}$	Area under the concentration-time curve from time zero (pre-dose) to last time of quantifiable concentration within a participant across all treatments
BE	Bioequivalence
BMI	Body mass index
BP	Blood pressure
BUN	Blood urea nitrogen
CI	Confidence Interval
CONSORT	Consolidated Standards of Reporting Trials
CV	Coefficient of variation
$C_{max}$	Maximum observed concentration
CPK	Creatine phosphokinase
CRF	Case Report Form
ECG	Electrocardiogram
FDA	Food and Drug Administration
FSH	Follicle Stimulating Hormone
GCP	Good Clinical Practice
GSK	GlaxoSmithKline
HBsAg	Hepatitis B surface antigen
HRT	Hormone replacement therapy
hCG	Human chorionic gonadotropin
HIV	Human Immunodeficiency Virus
h/hr	Hour(s)
ICF	Informed consent form
ICH	International Conference on Harmonization of Technical Requirements for Registration of Pharmaceuticals for Human Use
INR	International Normalized Ratio
IEC	Independent Ethics Committee
IgG	Immunoglobulin G
IP	Investigational Product
IRB	Institutional Review Board
kg	Kilogram
LAM	Local Affiliate Module
LDH	Lactate Dehydrogenase
LLN	Lower Limit of Normal

MCV	Mean corpuscular volume
MCH	Mean corpuscular hemoglobin
MedDRA	Medical Dictionary for Regulatory Activities
Mg	Milligrams
mL	Milliliter
MSDS	Material Safety Data Sheet
Msec	Milliseconds
PK	Pharmacokinetic
PT	Prothrombin Time
QTc	QT corrected
QTcB	QT interval corrected for heart rate according to Bazett's formula
RBC	Red blood cells
SAE	Serious adverse event(s)
SBP	Systolic Blood Pressure
SD	Standard deviation
SoA	Schedule of Activities
SOP	Standard Operating Procedure
SGOT	Serum glutamic-oxaloacetic transaminase
SGPT	Serum glutamic pyruvic transaminase
SmPC	Summary of Product Characteristics
t 1/2	Terminal phase half-life
Tmax	Time of occurrence of Cmax
ULN	Upper limit of normal
WBC	White blood cells
WCBP	Women of Childbearing Potential

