### Objectives and Endpoints:

Objectives	Endpoints
Primary  To determine if 500 mg Ciprofloxacin (GR37547) tablets are bioequivalent to reference 500 mg Ciprofloxacin tablets in healthy adult participants under fasting conditions.	Plasma PK parameters: $AUC_{(0-t)}$ and $C_{max}$ , for ciprofloxacin in relevant treatments.
Secondary  To assess secondary PK parameters of 500 mg ciprofloxacin tablets (GR37547) relative to reference 500 mg ciprofloxacin in healthy adult participants under fasting conditions.  To compare the safety and tolerability of a single dose of a 500 mg ciprofloxacin tablet (GR37547) with reference 500 mg ciprofloxacin tablet, in healthy adult participants under fasting conditions.	
 
Plasma PK parameters: <math>AUC_{(0-\infty)}</math>, <math>t_{max}</math>, <math>\%AUC_{ex}</math> and <math>t_{1/2}</math> for ciprofloxacin in relevant treatments.
 
Adverse events (AE), clinical laboratory values (Haematology and Biochemistry), ECGs and vital signs
 

AUC(0-∞)= Area under the concentration-time curve from time zero (pre-dose) extrapolated to infinite time; %AUCex= Percentage of AUC(0-∞) obtained by extrapolation; AUC(0-t)= Area under the plasma concentration versus time curve from time zero to t, where t is the time of the last quantifiable concentration; t1/2= Terminal phase half-life; Cmax= Maximum observed concentration; Tmax= Time of occurrence of Cmax.

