### Bioequivalence

The primary objective of this study is to demonstrate BE between the test 500 mg tablet formulation GR37547 and the reference formulation, based on PK endpoints  $C_{max}$  and  $AUC_{(0-t)}$  of ciprofloxacin.

The null hypothesis is that the true ratio of the geometric mean of the test treatment to the geometric mean of the reference treatment,  $\mu_{(Test)}/\mu_{(Reference)}$ , for the  $C_{max}$ , or  $AUC_{(0-t)}$ , is either  $<0.80$  or  $>1.25$  for plasma ciprofloxacin.

The alternate hypothesis is that the true ratio of the geometric mean of the test treatment to the geometric mean of the reference treatment for both the  $C_{max}$ , and  $AUC_{(0-t)}$ , is  $\geq 0.80$  and  $\leq 1.25$  for plasma ciprofloxacin.

Symbolically this is expressed as follows:

$$H_0: \mu_{(Test)}/\mu_{(Reference)} < 0.80 \text{ or } \mu_{(Test)}/\mu_{(Reference)} > 1.25$$

i.e., treatments are not bioequivalent.

versus

$$H_a: 0.80 \leq \mu_{(Test)}/\mu_{(Reference)} \leq 1.25$$

i.e., treatments are bioequivalent.

For each PK parameter designated as a primary endpoint, a two one-sided t-test (TOST)[[Schuirmann, 1987](#)] procedure with  $\alpha=0.05$  for each one-sided test will be used to test this set of hypotheses. Bioequivalence will be declared if the 90% CI for the true ratio of test to reference geometric means falls entirely within the range of 0.80 to 1.25 for all primary parameters.

For BE to be declared, the null hypothesis must be rejected, for all primary parameters  $C_{max}$ , and  $AUC_{(0-t)}$ , for ciprofloxacin.

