### 10.3.3. PK Parameters

Calculation of the PK parameters will be made with Phoenix WinNonlin 6.3 (Certara, L.P., [name]). The PK parameters will be calculated for each subject and treatment using non compartmental analysis and using the actual sampling time intervals (relative to IMP administration).

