#### 10.3.3.1. Primary Pharmacokinetic Parameters for ciprofloxacin

- Maximum observed plasma concentration ( $C_{\max}$ )
- Area under the plasma concentration versus time curve, from time zero to  $t$ , where  $t$  is the time of the last quantifiable concentration ( $AUC_{(0-t)}$ ).

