## **Presentation of PK Data, Descriptive Statistics and PK Assessment**

This section describes outputs to be presented.

The actual blood sampling times and time deviations will be listed for each participant dosed, treatment and scheduled sampling time. A listing of plasma concentrations of ciprofloxacin treatment will be provided.

Summary table reflecting summary statistics (n, arithmetic mean, geometric mean, median, coefficient of variation, standard deviation, minimum and maximum) per treatment will be provided for plasma concentrations of ciprofloxacin

Concentrations below the lower limit of quantification (LLOQ) will be indicated as below the limit of quantification (BLQ). These BLQ concentrations will be handled as follows:

- For descriptive statistics, pre-dose BLQ concentrations will be substituted by zeros. All other BLQ values will be substituted by  $\frac{1}{2}$ LLOQ value before the calculation of the summary statistics. Values reported as 'NS' (no sample) will be set to "missing".
- For PK assessment, all BLQ values at pre-dose and in the absorption phase, before the first reported concentration, will be substituted by zeros. The BLQ values between evaluable concentrations will be substituted by  $\frac{1}{2}$ LLOQ, before the calculation of the PK parameters. The terminal BLQ values will be set to missing. These measures are taken to prevent an over-estimation of AUC.

- For PK calculations, missing concentrations will be deleted, resulting in an interpolation between the nearest two concentration values.

A listing for PK parameters of ciprofloxacin per treatment will be provided. A summary table reflecting summary statistics (n, arithmetic mean, geometric mean, median, coefficient of variation, standard deviation, minimum and maximum) per treatment will be provided for PK parameters of ciprofloxacin.

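### Does the different wording of AUC(0-t) in the abbreviation list leave the co-primary endpoint undefined?

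*Combined protocol and SAP*

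**What the plan says.** The Synopsis (Objectives and Endpoints) defines AUC(0-t) as the area "from time zero to t, where t is the time of the last quantifiable concentration". Table 3 in Section 4 repeats this, and Section 10.3.3.1, which lists the primary parameters, says that t "is the time of the last quantifiable concentration".

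Section 10.3.3 sets the unit of calculation: "The PK parameters will be calculated for each subject and treatment using non compartmental analysis". Section 10.3.1 says the same. Appendix 6, the analysis plan to which Section 10 sends the reader, adds a rule for the end of the profile: "The terminal BLQ values will be set to missing".

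Appendix 7, the abbreviation list, describes the same symbol as running "to last time of quantifiable concentration within a participant across all treatments". Nothing in the documents reconciles this with the other definitions.

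Section 10 (Bioequivalence) makes AUC(0-t) decisive alongside Cmax: "For BE to be declared, the null hypothesis must be rejected, for all primary parameters".

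**The concern.** A shared end time and a per-profile end time are different estimators. Suppose a participant is still quantifiable at 24 h on Reference but only to 18 h on Test. The per-profile version then compares areas over unequal intervals, while a shared time would compare areas over the same interval. If one product falls below the quantification limit earlier more often than the other, the two versions differ systematically.

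The study is open label, and failure on AUC(0-t) alone means bioequivalence is not declared. Two definitions of such an endpoint in one protocol could look like room to choose after the data are seen.

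**Working it through.** **1. The definitions side by side**

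| Place | What it fixes | Implied end time |
|---|---|---|
| Synopsis; Table 3; Section 10.3.3.1 | definition of AUC(0-t) | last quantifiable concentration |
| Sections 10.3.1 and 10.3.3 | calculation by participant and treatment | each profile's own |
| Appendix 6, BLQ rules | terminal BLQ values dropped | each profile's own |
| Appendix 7 | abbreviation only | shared across treatments |

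The Appendix 7 wording cannot be carried out as it stands. It does not say outright whether the shared time is the earlier or the later of the two. If it is the later, the shorter profile has no value there, because Appendix 6 has set it to missing and gives no rule for filling it.

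**2. The plan's own figure**

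Section 10.1 gives 22 evaluable participants (CV 18%, ratio 0.95, limits 80-125%, one-sided alpha 0.05, power 90%). Exact two one-sided tests power for a 2x2 crossover, with log-scale SD = sqrt(ln(1 + 0.18²)), SE = SD × sqrt(2/N) and N - 2 degrees of freedom, is 0.899 at N = 20 and 0.924 at N = 22. The figure of 22 reproduces, and it does not depend on which end time is used.

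**3. Effect on one participant**

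Inputs: half-life 4-7 h and Cmax 1.5-2.9 mg/L (Section 3.2); last samples at 12, 18 and 24 h (Table 1). With mono-exponential decline, the 18-24 h segment relative to AUC(0-18), for half-life h, is

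(2^(-18/h) - 2^(-24/h)) / (1 - 2^(-18/h))

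- h = 4: (0.0442 - 0.0156) / 0.9558 = 3.0%
- h = 7: (0.1682 - 0.0929) / 0.8318 = 9.1%

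The trapezoidal rule at the protocol's sampling times (one-compartment profile, assumed absorption rate 2.5/h) gives the ratio for otherwise identical profiles ending at 18 h on Test and 24 h on Reference:

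| Half-life | Per-profile ratio | Shared-time ratio | Factor on the 22-participant geometric mean ratio |
|---|---|---|---|
| 4 h | 0.966 | 1.000 | 0.966^(1/22) = 0.998 |
| 5 h | 0.946 | 1.000 | 0.946^(1/22) = 0.997 |
| 7 h | 0.911 | 1.000 | 0.911^(1/22) = 0.996 |

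Each such participant therefore moves the trial ratio by about 0.2-0.4%. When both profiles end at the same sample, the difference is exactly zero.

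**4. How often profiles would end at different samples**

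This depends on the quantification limit, which the documents do not give; Section 9.5 refers to a separate bioanalytical protocol. Taking the peak at 1.5 h, the predicted 24 h concentration is Cmax × 2^(-22.5/h). It runs from 1.5 × 0.0203 = 0.03 mg/L to 2.9 × 0.1077 = 0.31 mg/L.

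Trials of 22 were simulated, 300 per setting, with mean half-life 5 h and within-participant AUC CV about 11.5% (Section 10.1 gives 11-12%):

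| Assumed limit (mg/L) | Participants ending at different samples | Mean shift in ratio | Largest shift in any trial | Conclusion differs, true ratio 0.95-1.00 | Conclusion differs, true ratio 0.85 |
|---|---|---|---|---|---|
| up to 0.02 | at most about 1% | about 0% | 0.3% | 0% | 0-1% |
| 0.05 | 7-10% | 0.0-0.3% | 1.3% | 0% | 4% |
| 0.1 | 16-22% | 0.0-1.2% | 3.8% | 0-0.3% | 19% |
| 0.2 | 20-25% | 0.0-2.7% | 6.5% | 0-2% | 28% |

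The CV assumption matters. In runs that let exposure and half-life vary more within participants, at a true ratio of 0.95, the conclusion differed in 0% of trials at limits up to 0.02 mg/L, 0.7% at 0.05, 10% at 0.1 and 21% at 0.2.

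**5. Direction**

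Where the versions differed systematically, the per-profile ratio was further from 1. At a true ratio of 0.85 and a limit of 0.2 mg/L, it averaged 0.828, against 0.850 with a shared time. The definition in the operative text is therefore the more demanding one.

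**The case for a change.** The strongest case for acting is that the conflict is genuine, concerns a co-primary endpoint and could be removed by editing one line. The added condition in Appendix 7 is too specific to be a loose paraphrase. Discordant end times cannot be ruled out without knowing the quantification limit. With a high limit, and either a true ratio of 0.85 or wider within-participant variability, the two versions would disagree on bioequivalence in an appreciable share of trials.

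All of that stands as description. What does not stand is that an analyst could adopt either version and claim to follow the plan. A shared time would go against the per-profile calculation in Sections 10.3.1 and 10.3.3 and, if the later time were used, would need a BLQ rule that the plan lacks. It would rest on a glossary entry alone.

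The larger effect sizes also need care. A shift of 0.6-1.7% in the overall ratio assumes that 20% of participants are discordant in the same direction, and the documents give no basis for that. The 9.1% for one participant belongs to a 7 h half-life, where the 24 h level is 10.8% of Cmax, so such a profile would usually still be quantifiable. Profiles that drop out early tend to have short half-lives, where the segment is small (3.0% at 4 h). The pre-dose rule in Section 10.3.1, which compares concentrations with 5% of Cmax, suggests by inference an assay that can measure down to that level. At a limit of exactly 5% of Cmax, a typical profile is lost at 24 h only if the half-life is below about 5.2 h, where the segment adds about 5.5%.

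A shared-time analysis could be added as a sensitivity analysis, but that is a preference. Table 7 already analyses AUC(0-∞) by the primary method, and %AUCex is summarised, so unequal truncation would be visible.

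**Conclusion.** No change to the plan follows. The Appendix 7 entry is a clerical inconsistency; the objectives, Section 10 and Appendix 6 together fix one computable estimator, with t taken from each profile. Aligning the glossary would leave the endpoint, model, sample size of 22 and decision rule as they are.

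This conclusion rests mainly on the text and does not need the effect to be negligible. As to size, the difference is zero where both profiles end at the same sample and about 0.2-0.4% of the trial ratio per discordant participant. Under the planned ratio and the plan's AUC variability, it changed the conclusion in at most 2% of simulated trials. That last figure assumes a quantification limit of 0.005-0.2 mg/L, within-participant AUC CV of about 11.5% and one-compartment profiles. It rises with wider variability or a true ratio near 0.85 if the limit is 0.1 mg/L or more, and in the systematic cases the operative definition is the stricter of the two.

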### Trademark Information

Trademarks of the GlaxoSmithKline group of companies	Trademarks not owned by the GlaxoSmithKline group of companies
CIPVAL	Ciproxin Phoenix SAS WinNonlin
